6 METHODS OF ASSESSMENT

Demographic Data

At Visit 1 (Screening), subject demographic data will be collected. These include: date of birth, gender and race.

Medical History

At Visit 1 (Screening) a complete medical history, including prior interventions to the study knee, will be obtained from each subject.

Concomitant Medications

Detailed history of medications will be documented for each subject at Visit 1 (Screening) and Visit 2 (Baseline). Concomitant medications (especially any changes in medication) will be documented for each subject at each scheduled visit.

Kellgren-Lawrence Grading Scale

Radiographic images should be evaluated according to the Kellgren-Lawrence Grading Scale as noted below in [Figure 2](#).

FIGURE 2: Kellgren-Lawrence Grading System

Grade	Description
0	Normal knee without osteophytes or joint space narrowing
1	Possible osteophytic lipping and doubtful narrowing of joint space
2	Definite osteophytes and possible narrowing of joint space
3	Moderate multiple osteophytes, definite narrowing of joint space and some sclerosis and possible deformity of bone ends
4	Large osteophytes, marked narrowing of joint space, severe sclerosis and definite deformity of bone ends

Physical Examination and Vital Signs

Height in feet and inches will be measured at Visit 1 (Screening).

Body weight in pounds (lb) will be measured at Visit 1 (Screening) and at Visit 7 (Week 12 or Early Termination Visit).

Body temperature (deg F) will be measured at each visit.

Systolic and diastolic BP and pulse rate will be measured with the subject in a seated position.

The full physical examination will consist of examining the following body systems: cardiovascular, respiratory, abdominal, skin and musculoskeletal other than the knee. The

physical examination of the target knee will consist of evaluating the knee joint for effusion and tenderness on palpation.

Laboratory Assessments

Blood will be collected at Screening and Week 12 and analyzed by a local lab. Reference ranges must be available to evaluate lab values during the course of the study.

See [Table 6.1](#) for full schedule of assessments and procedures

6.1 EFFICACY ASSESSMENTS

Note: Efficacy questionnaire questions will be asked “with reference to study knee” i.e. to obtain scores specific for the treated knee.

6.1.1 WOMAC® Osteoarthritis Index (Bellamy 1988)

WOMAC Index 3.1 (sections A-C), using the 5-point Likert scale, should be completed by subjects at Screening, pre-dose and pre-aspiration as applicable on Day 0 and at Weeks 2, 6, 10 and 12. All subjects are required to take at least 5 minutes to complete the questionnaire. Subjects are asked about their pain, stiffness, and function in the knee (study joint) due to arthritis during the last 24 hours.

Subjects respond to each subscale by using a 5-point Likert score (0 = none, 1 = mild, 2 = moderate, 3 = severe, 4 = extreme).

6.1.2 Patient’s Global Assessment of Disease Severity (PGA)

The PGA should be completed by subjects at Screening, pre-dose and pre-aspiration as applicable on Day 0 (prior to injection), and at Weeks 2, 6, 10 and 12.

Subjects are asked the following question: “Considering all the ways in which your arthritis affects you, please indicate how you are doing.”

Subjects respond by using a 5-point adjectival Likert score (0 = very well, 1 = well, 2 = fair, 3 = poor, 4 = very poor).

6.2 SAFETY PARAMETERS

Based on results of previous studies of a single intra-articular injection of Ampion™ < 5 kDa ultrafiltrate of 5% HSA in adults with OA of the knee in which no clinically significant differences between active and saline were found, safety will be assessed by recording adverse events, vital signs, results of physical examination, recording prior and concomitant medications and safety labs.

6.2.1 Vital Signs

Vital signs (radial pulse rate, blood pressure, and body temperature) should be recorded at Screening, pre- and post-treatment on Day 0, and then on visits at Weeks 6 and 12.

Vital signs should be taken after the subject has rested in a seated position for at least 5 minutes.

6.2.2 Clinical laboratory tests

Subjects in the will undergo a blood draw at Screening and Week 12. Blood draws should be done after subject meets all other inclusion/exclusion criteria at Screening; Blood draws should be done at Week 12 after all WOMAC and PGA assessments are completed. All clinically significant values will be followed up at the Investigator's discretion. Blood laboratory results must be reviewed and compared to reference ranges throughout the study to evaluate for potential adverse events. Blood draws will be performed in compliance with standard laboratory procedures.

The following analysis will be conducted by the local laboratory:

Serum biochemistry: Sodium, potassium, chloride, bicarbonate, glucose, urea, creatinine, creatine kinase, urate, phosphate, total calcium, cholesterol, albumin, globulins, protein, total bilirubin, conjugated bilirubin, gamma glutamyltransferase (GGT), alkaline phosphatase (ALP), alanine aminotransferase (ALT), aspartate aminotransferase (AST) and lactate dehydrogenase (LD).

Hematology: Hemoglobin, red blood cell count, hematocrit, mean cell volume (MCV), mean cell hemoglobin (MCH), mean cell hemoglobin concentration (MCHC), platelets, white cell count, neutrophils, lymphocytes, monocytes, eosinophils, and basophils.

In addition to the tests stated above, all female subjects with child-bearing potential will be tested for serum hCG (for exclusion #12/pregnancy).

TABLE 6.1 SCHEDULE OF ASSESSMENTS AND PROCEDURES

	Screening VISIT 1	Baseline Randomization Treatment VISIT 2	Post-treatment check (telephone contact) VISIT 3	Week 2 (telephone contact) VISIT 4	Week 6 VISIT 5	Week 10 (telephone contact) VISIT 6	Week 12 Final Visit VISIT 7	Early Termination
Visit # Day	1 Day-7 to 0	2 Day 0	3 Day 1	4 Day 14 ± 7	5 Day 42 ± 7	6 Day 70 ± 7	7 Day 84 ± 7	
Informed Consent	X							
Inclusion/exclusion criteria	X	X						
Medical history/prior medications ²	X						X	X
Concomitant medications	X	X	X	X	X	X	X	X
Physical examination*	X*	X			X		X*	X*
Vital Signs	X	X			X		X	X
Randomization		X						
WOMAC A-C, 5-point Likert Scale	X	X		X	X	X	X	X
Patient's global assessment (PGA)	X	X		X	X	X	X	X
X-ray ¹	X							
Clinical laboratory tests	X						X	X
Treatment with study drug		X						
Rescue medication dispensed/collected		X					X	X
Review Rescue medication			X	X	X	X	X	X
Adverse Events		X	X	X	X	X	X	X

Visits are in clinic except for Day 1 and Weeks 2 and 10 when subjects will be contacted by telephone

1 X-ray must be acquired at Screening to satisfy inclusion criteria #5. X-rays obtained within 6 months of screening are acceptable.

2 At Week 12 and Early Termination visits, ask subject if they have previously sought out treatment for OAK prior to this study

*Includes height and weight at Screening (Visit 1) and Week 12 (Visit 7)

7 DISCONTINUATION CRITERIA

7.1 EARLY DISCONTINUATION OF THE STUDY

It is agreed that for reasonable cause, either the investigator or the Sponsor may terminate this study, provided a written notice is submitted at a reasonable time in advance of intended termination; if by the investigator notice is to be submitted to Ampio Pharmaceuticals, Inc., and if by the Sponsor, notice will be provided to each investigator.

If a severe local reaction or drug-related SAE occurs at any time during the study, the Safety Monitoring Committee will review the case immediately.

The study will be immediately suspended and no additional Ampion treatments administered pending review and discussion of all appropriate study data by the SMC if 1 or more subjects develop any of the following adverse events deemed to be possibly, probably, or definitely related to Ampion by the Investigator and/or Medical Monitor, based upon close temporal relationship or other factors:

- Death
- Anaphylaxis (angioedema, hypotension, shock, bronchospasm, hypoxia, or respiratory distress)
- Induction of autoimmune arthritis
- Hepatic failure
- Aplastic anemia.

The study will not be restarted until all parties have agreed to the course of action to be taken and the IRB/EC has been notified.

7.2 EARLY DISCONTINUATION OF INDIVIDUAL SUBJECTS

Subjects are to be withdrawn from the study for any of the following reasons:

- Withdrawal of informed consent
- Subject is lost to follow up.

Subjects will also be withdrawn at any time if the investigator concludes that it would be in the subject's best interest for any reason. Protocol violations do not lead to subject withdrawal unless they constitute a significant risk to the subject's safety.

Subjects can voluntarily withdraw from the trial for any reason at any time. They are to be considered withdrawn if they state an intention to withdraw, fail to return for visits, or become lost to follow up for any reason. Subjects withdrawing from the study because of an AE should be followed for at least 30 days, resolution of the AE or until no further improvement is expected, whichever comes first.

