5.1.6 Visit 6 (Week 10 ± 7 days, telephone contact)

The following procedures will be performed at Visit 6:

- Perform WOMAC (sections A-C), using the 5-point Likert scale for the evaluation of the study knee.
- Perform PGA evaluation of the study knee.
- Record AEs.
- Record concomitant medications.
- Review rescue medication use.

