5.1.8 Early Termination Visit

The following procedures will be performed at Early Termination Visit:

- Perform and record physical examination, including weight.
- Record vital signs. (Measure body temperature, systolic / diastolic blood pressure [BP] and pulse rate).
- Perform WOMAC (sections A-C), using the 5-point Likert scale for the evaluation of the study knee.
- Perform PGA evaluations of the study knee.
- Collect blood sample for laboratory assessment.
- Record AEs.
- Obtain information from subject about medical care for knee OA prior to participation in the current study (medical history).
- Record concomitant medications.
- Review, count, and collect rescue medication.

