8 TREATMENT

Eligible subjects will be randomized (6:1) to a single 4 mL Ampion intra-articular injection or a single 4 mL saline injection into the study knee.

Subjects will be randomized to an assigned subject number after confirmation of eligibility, just prior to treatment.

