9.3 RECORDING OF ADVERSE EVENTS AND SERIOUS ADVERSE EVENTS

Recording and reporting of adverse events should be in accordance with the FDA final “Guidance for Industry and Investigators Safety Reporting Requirements for INDs and BA/BE Studies” of December 2012.

Any AE is to be recorded in the eCRF. In order to avoid vague, ambiguous, or colloquial expressions, the AE should be recorded in standard medical terminology rather than the subject’s own words. Whenever possible, the investigator should combine signs and symptoms that constitute a single diagnosis.

The existence of an AE may be concluded from a spontaneous report of the subject; from the physical examination; or from special tests e.g., laboratory assessments, where applicable, or other study-specified tests (source of AE).

The reporting period begins from the time that the subject receives IA injection at the Baseline visit through subject’s Final Visit at 12 weeks. Any events continuing at study exit will be followed for 30 days or to resolution, or until no improvement is expected, whichever comes first. Any SAE occurring after the reporting period must be promptly reported if a causal relationship to the investigational drug is suspected. If the subject begins a new therapy, the safety reporting period ends at the time the new treatment is started, however, death must always be reported when it occurs during the 12-week study period, irrespective of intervening treatment.

Each AE is to be evaluated for duration, severity, seriousness, and causal relationship to the investigational drug. The action taken and the outcome must also be recorded.

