10.3.11 Data presentation**10.3.11.1 Demographic and Baseline Characteristics:**

Demographic (e.g., age, sex, race, and ethnicity) and Baseline characteristics (e.g., weight, height, prior injection of another intra-articular therapeutic for OA of the knee) summarized using descriptive statistics, overall and by treatment group for the ITT analysis population.

10.3.11.2 Medical History and Physical Examination:

The number and percent of subjects with past and current medical disorders at the time of randomization will be presented overall for the ITT analysis population. Results of any abnormalities documented from the abbreviated physical examination at Baseline and Week 12, will be summarized overall for the safety and ITT analysis populations.

10.3.11.3 Concomitant Medications or Treatments:

The number and percent of subjects receiving concomitant medications or treatments prior to and during the study and at the final visit will be tabulated and presented overall for the ITT

analysis population. Concomitant medications/treatments will be summarized using descriptive statistics and will be presented by type of drug (WHO DRUG classification) overall for the safety and ITT analysis populations.

10.3.11.4 Safety data:

Safety data will be evaluated by changes in vital sign measurements, physical exam, laboratory analysis, and the frequency and severity of AEs. Concomitant medication will be recorded for safety.

Adverse events:

The Investigator is responsible for monitoring the safety of subjects who have enrolled in the study. All AEs considered related, or possibly related to Ampion™, will be followed until the event resolves or stabilized without further change. Subjects will be followed for the occurrence of AEs until 12 weeks after the first dose of study medication.

Investigators are required to document all AEs occurring during the clinical trial, commencing with the first day of treatment through the end of study. AEs should be properly documented on the appropriate CRF pages.

The severity of AEs (mild, moderate, severe), relatedness (related, possibly related, unrelated) along with the duration, action taken, and outcome (e.g., study withdrawal) will also be recorded. In addition, events meeting the criteria of a Serious Adverse Event (SAE) must be reported to the Sponsor within 24 hours on the SAE reporting forms.

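### Withdrawal after the single Day 0 injection leaves no planned Week 12 WOMAC or PGA, and no scheduled contact for new AEs, in subjects who still consent to contact

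*Protocol*

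**What the plan says.** - **Treatment.** Protocol 8: "Eligible subjects will be randomized (6:1) to a single 4 mL Ampion intra-articular injection or a single 4 mL saline injection into the study knee". There is no later dose.
- **Withdrawal.** Protocol 7.2 lists withdrawn consent and loss to follow-up as reasons, then adds: "Subjects will also be withdrawn at any time if the investigator concludes that it would be in the" subject's best interest. Of subjects who leave voluntarily it says: "They are to be considered withdrawn if they state an intention to withdraw, fail to return for visits, or become lost to follow up". It has no status for someone who stops clinic visits but agrees to be contacted.
- **Last assessment.** Protocol 5.1.8 ("The following procedures will be performed at Early Termination Visit") includes WOMAC A-C, PGA and AEs. Nothing is scheduled after it. SAP 5.2 places the end of study at Day 84 ± 7 unless the subject terminated early.
- **AEs.** Protocol 7.2: "Subjects withdrawing from the study because of an AE should be followed for at least 30 days", or until resolution or no expected improvement, whichever is first. Protocol 10.3.11.4, repeated in SAP 4.9.4: "Subjects will be followed for the occurrence of AEs until 12 weeks after the first dose of study medication". Protocol 9.3 runs the reporting period to the Week 12 visit and requires later SAEs to be reported if causality is suspected. It also states: "If the subject begins a new therapy, the safety reporting period ends at the time the new treatment is started".
- **Telephone outcomes.** At the Week 10 call (Protocol 5.1.6) the site is to "Perform WOMAC (sections A-C), using the 5-point Likert scale for the evaluation of the study knee". PGA is taken on the same call, and both are also taken by telephone at Week 2.
- **Missing data.** Protocol 10.4 and SAP 4.10 impute a missing Week 12 score in the ITT population by worst observation carried forward (WOCF), with multiple imputation and last observation carried forward (LOCF) as sensitivity analyses. Protocol 10.3.3 removes anyone without a Week 12 visit from the per-protocol set.

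**The concern.** In a multi-dose trial, leaving treatment and leaving the study are different events. Here the first cannot happen after Day 0, so a withdrawal decision only stops data collection. A subject withdrawn at, say, Week 4 has a last score about 8 weeks before the primary time point, although the protocol already accepts the needed questionnaires by telephone. Withdrawals decided by the investigator or prompted by an AE are plausibly related to outcome.

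The primary test compares the Ampion proportion with a fixed 30%, and Protocol 10.1.1 rules out comparison with the concurrent saline arm. Whatever is put in place of a missing outcome therefore acts directly on the tested proportion. On safety, the withdrawn subject stays in the safety population (Protocol 10.3.1), but no planned contact would reveal a new AE between the Early Termination visit and Week 12, other than what surfaces while an existing AE is followed.

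**Working it through.** **Inputs.** n = 146 Ampion, null 30%, planning rate 45%, one-sided alpha 0.025, exact binomial test (Protocol 10.3.4 and 10.3.7, SAP 2.4). Previous combined KL 4 Ampion responder rate 58.6% (Protocol Table 1.5.3). Enrolled n equals powered n, and no dropout allowance is given. *Assumed:* k = 7, 15, 22 or 29 Ampion subjects withdrawn, about 5%, 10%, 15% and 20% of 146.

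**1. The plan's own figure.** The pass mark is the smallest r with P(X ≥ r | 146, 0.30) ≤ 0.025. At r = 55 the tail is 0.0284 and at r = 56 it is 0.0189, so r = 56. Power is P(X ≥ 56 | 146, 0.45) = 95.6%. The stated power above 90% is correct with complete data.

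**2. Primary ITT analysis, extreme case of WOCF.** Count all k as non-responders, with response among them otherwise at the overall rate. Power = P(X ≥ 56 | 146 − k, p).

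| k lost | 146 − k | Expected responders at 45% | Power at 45% | Power at 58.6% |
|---|---|---|---|---|
| 0 | 146 | 65.7 | 95.6% | >99.9% |
| 7 | 139 | 62.6 | 88.6% | >99.9% |
| 15 | 131 | 59.0 | 72.7% | >99.9% |
| 22 | 124 | 55.8 | 52.0% | 99.9% |
| 29 | 117 | 52.7 | 29.8% | 99.3% |

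**3. Direction under the null.** At a true 30% with k = 15 counted as non-responders, P(X ≥ 56 | 131, 0.30) = 0.13%, against 1.89% with none missing. The primary analysis becomes harder to pass, not easier.

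**4. Per-protocol set.** Let the overall true rate be 30% and the 15 withdrawn subjects all be true Week 12 non-responders, with no other exclusions. The 0.30 × 146 = 43.8 expected responders then sit among 131 completers, a rate of 43.8/131 = 33.4%. The pass mark at n = 131 is 51, and P(X ≥ 51 | 131, 0.334) = 10.8%. With k = 7 the figure is 5.8%.

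**5. LOCF.** Same truth, but 45% of the 15 were responders at their last observation (assumed). Expected count = 43.8 + 0.45 × 15 = 50.55. The chance that Binomial(131, 0.334) + Binomial(15, 0.45) reaches 56 is 19.3%. With k = 7 it is 6.6%.

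**6. Same truth with Week 12 observed.** The 15 are recorded as the non-responders they are, and the ITT test rejects with probability P(X ≥ 56 | 131, 0.334) = 1.6%, below 2.5%.

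**The case against.** The strongest reply is that a conservative primary rule is already in place. That stands: a reader might infer that early withdrawal inflates the primary result, but step 3 shows the opposite when withdrawn subjects count as non-responders. One qualification is that neither document says whether Baseline counts as an observation for WOCF, so the all-non-responder case is the extreme and not a certainty.

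A reader might also infer that withdrawal ends all AE collection, or that 7.2 flatly contradicts 10.3.11.4. The text does not support either. Section 7.2 itself continues follow-up of the AE, 9.3.1 and 10.3.11.4 follow related AEs, and 9.3 captures later suspected-related SAEs. The 12-week statement has no exception for withdrawn subjects. What is missing is a scheduled contact that would carry it out, and a reconciliation with the new-therapy cut-off in 9.3.

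It is tempting to set 15 imputed outcomes against the margin of about 10 between 65.7 expected responders and the pass mark of 56. These are unlike quantities: at 45% only 0.45 × 15 = 6.75 of the 15 would have responded, and the expected count stays above 56 until about 22 are lost.

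It is also fair that:
- No sentence forbids later contact. The gap is read from silence, the Early Termination procedures and the SAP end-of-study definition.
- An AE is not a listed reason for withdrawal, and 7.2 limits withdrawal for protocol violations.
- The fix cannot reach subjects who are lost or refuse contact, so the recoverable group may be small.
- If those withdrawn are true non-responders, observing them restores no power. It then serves to make the supportive analyses reliable.

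**Conclusion.** The point holds as an avoidable loss of obtainable data. Following the plan as written, a withdrawn but consenting subject contributes no Week 12 WOMAC or PGA and has no scheduled contact for new AEs to Week 12. The main cost to the primary ITT test is power at the sponsor's planning value: 95.6% to 88.6% with 7 lost and 72.7% with 15, if all count as non-responders and would otherwise have responded at 45%. At the previous KL 4 rate of 58.6% the loss is negligible, with power above 99% even at 29 lost.

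With withdrawn subjects counted as non-responders in the primary analysis, favourable error is confined to the supportive analyses: about 11% (per-protocol) and 19% (LOCF) rejection at a true 30% with 15 withdrawn non-responders. These are the analyses meant to back up the primary result. All withdrawal numbers and response rates among withdrawn subjects are assumptions, so the actual size cannot be fixed from the documents.

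**What to change.** In Protocol 7.2 and 5.1.8, separate stopping clinic visits from withdrawing consent to further contact. Unless consent to contact is withdrawn, obtain WOMAC A-C, PGA, new AEs and new treatments at Day 84 ± 7, in clinic or by telephone as at Weeks 2 and 10. Align the end-of-study definition in SAP 5.2. In Protocol 10.4 and SAP 4.10, state that an observed Week 12 score is used in the ITT analysis and that imputation applies only when it could not be obtained. Reconcile the AE windows in Protocol 7.2, 9.3 and 10.3.11.4 and SAP 4.9.4, so that it is clear how long new AEs are sought after withdrawal and after a new therapy starts.

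The cost is a short amendment, matching consent wording and one call per withdrawn subject. The downside is that some Week 12 scores will come by telephone where the plan has an in-clinic visit.

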5.1.11 CONCOMITANT MEDICATIONS AND RESCUE MEDICATION

The following medications/therapies are NOT allowed during this clinical study:

1. No IA injected medications in the study knee during the study.
2. No analgesics containing opioids.
3. NSAIDs may not be used during the study (low-dose Aspirin (81 mg) is allowed). Acetaminophen is available as a rescue medication during the study from the provided supply.
4. No non-pharmacological treatment targeting OA started or changed during the study.
5. No topical treatment on the study knee during the study.
6. No significant anticoagulant therapy (e.g. Heparin or Lovenox) during the study (treatment such as low-dose Aspirin (81 mg) or Plavix is allowed)
7. No systemic treatments that may interfere with safety or efficacy assessments during the study.
8. No immunosuppressants.
9. No use of systemic or intra-articular corticosteroids
10. No human albumin treatment during the study.

Any medication used during the study should be recorded. All concomitant medication start and stop dates, total daily dose, route and indication should to be recorded.

The only allowed analgesia medication during the 12-week study is 500 mg of acetaminophen, 1 tablet every 4 hours as required by the subject, not to exceed 3,000 mg of acetaminophen in a 24-hour period. Dose must be reduced if using other medications that contain acetaminophen (cold medicines, etc.).

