10.3 ANALYSIS POPULATIONS

10.3.1 Safety Analysis Population:

The safety analysis population is defined as all subjects who receive study medication (Ampion or saline). Subjects will be analyzed as treated.

10.3.2 Intent-to-treat Population:

The intent-to-treat (ITT) analysis population is defined as all subjects who are randomized, regardless of whether or not they have received the investigational product, or have a post-baseline visit. All efficacy analyses will be performed in the ITT population. Subjects will be analyzed as treated.

10.3.3 Per Protocol Population:

The per protocol analysis population is defined as all subjects included in the ITT analysis who met all entry criteria, completed the Week 12 visit, and had no major protocol violations. All efficacy analyses will be repeated in the per-protocol population. These analyses will be supportive of the ITT analysis. Subjects will be analyzed as treated.

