10.3.4 Hypotheses Tested

For the primary endpoint of the proportion of patients who are responders according to the OMERACT-OARSI criteria, the following hypothesis will be tested.

$H_0: \pi \leq \pi_0$ versus $H_A: \pi > \pi_0$

Where π_0 is the hypothesized value for the proportion of responders. The value will be 30% in this study. This test will be tested using an exact binomial test. That is, given the sample size of n , the number of responders X , and the value of $\pi_0 = 0.30$, then probability that X or more events would be observed will be calculated as the p-value. Since this is a one sided test, the alpha level will be 0.025.

The primary hypothesis and these secondary hypotheses will be tested in a hierarchical manner with the primary first and the secondary hypotheses in the order listed. Using this approach, there is no adjustment necessary in the overall significance level. All testing will be conducted using an overall significance level of 5%. If the tests are one sided, the significance level will be 2.5%.

The secondary endpoints are represented by the proportion of patients who are responders as identified by the following response criteria:

- Improvement in pain and function (WOMAC A and WOMAC C) over baseline of $\geq 20\%$ and a 0.5 point absolute change
- Improvement in patient global assessment (PGA) over baseline of $\geq 20\%$ and a 0.5 point absolute change in PGA
- Improvement in pain and function (WOMAC A and WOMAC C) over baseline of $\geq 20\%$ and a 0.5 point absolute change compared to saline

The hypotheses for the first two secondary endpoints are identical and are:

$H_0: \pi \leq 30\%$ versus $H_A: \pi > 30\%$

These will be tested using the exact binomial test.

The hypothesis for the third secondary endpoint will be tested as:

$H_0: \pi_A \leq \pi_{HS}$ versus $H_A: \pi_A > \pi_{HS}$

Where π_A is the response rate from Ampion in this study and π_{HS} is the response rate of the saline control from previous single-injection Ampion studies. This will be tested using Fisher's exact test.

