10.4 MISSING DATA

All data collected under this study protocol will be included in the assessment of subject safety. Missing or incomplete AE data will assume greatest relationship to study drug and/or severity.

For the primary effectiveness endpoint (WOMAC A, WOMAC C, and PGA), missing Week 12 values will be imputed when the ITT analysis population is used. Worst Observation Carried Forward (WOCF) will be selected as the primary method of imputing missing 12 Week data. Alternate imputation methods employed will include multiple imputations (SAS PROC MI and SAS PROC MIANALYZE) and Last Observation Carried Forward (LOCF). These sensitivity analyses will be conducted for the primary effectiveness endpoint, to ensure that the primary method of imputation chosen is robust with respect to imputation method used.

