3. PRIMARY STUDY ENDPOINTS

3.1 Primary Endpoint

The primary trial endpoint is to evaluate improvement of OMERACT-OARSI response of a single 4 mL Ampion[™] intra-articular injection from Baseline to Week 12.

A patient in this study will be considered an OMERACT-OARSI responder for the purpose of efficacy analysis if the following criteria is met:

- 1) The patient has a percent improvement in pain (WOMAC pain) from baseline of $\geq 50\%$ and an absolute change in pain from baseline of ≥ 1 point or the patient has a percent improvement in function (WOMAC function) from baseline of $\geq 50\%$ and an absolute change in function from baseline of ≥ 1 point. Meeting this criterion designates the patient as a responder. If the patient does not meet this criterion, then
- 2) The patient demonstrates improvement in at least 2 of the following:
 - Improvement in pain (WOMAC A) over baseline of $\geq 20\%$ and a 0.5 point absolute change in pain
 - Improvement in function (WOMAC function) over baseline of $\geq 20\%$ and a 0.5 point absolute change in function
 - Improvement in patient global assessment (PGA) over baseline of $\geq 20\%$ and a 0.5 point absolute change in PGA

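### No planned analysis counts a subject who takes barred treatment before Week 12 as a non-responder, although the Ampion arm alone is tested against a fixed 30%

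*Protocol*

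**What the plan says.** Protocol 5.1.11 lists treatments that are not allowed during the study. They include injections into the study knee, opioids, NSAIDs, topical treatment on the study knee, and steroids: "No use of systemic or intra-articular corticosteroids". Protocol 7.2 says what follows from a breach: "Protocol violations do not lead to subject withdrawal unless they constitute a significant risk" to the subject's safety. A subject who takes a barred treatment will therefore normally stay and give a Week 12 score.

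Protocol 10.3.2 defines ITT as all randomized subjects and places all efficacy analyses there. Response is defined in SAP 3.1 ("A patient in this study will be considered an OMERACT-OARSI responder for the purpose of efficacy analysis if the following criteria is met") and Protocol 10.2. The criteria that follow are thresholds for change in WOMAC pain, WOMAC function and PGA, and none refers to other treatment. On imputation, Protocol 10.4 says "missing Week 12 values will be imputed when the ITT analysis population is used", and SAP 4.10 matches it. Worst observation carried forward, multiple imputation and last observation carried forward all act on missing values only.

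The per-protocol (PP) set in Protocol 10.3.3 is limited to subjects who met entry criteria, "completed the Week 12 visit, and had no major protocol violations". Neither document defines a major violation.

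Protocol 10.3.4 tests the responder proportion against a fixed value: "The value will be 30% in this study". SAP 2.3 says that the saline arm is not meant for analysis.

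**The concern.** Take a subject with no relief who has a barred injection in the study knee at Week 8 and scores better at Week 12. Under the plan as written, a score that meets the thresholds makes this subject an Ampion responder in the ITT analysis. No sentence says that such scores count. The result follows because no rule says otherwise.

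Two features make this matter here. First, the primary and first two secondary tests have no concurrent comparator. In a two-arm comparison, use of other treatment in both arms would partly offset. Against a fixed 30%, each response produced by another treatment adds to the tested rate.

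Second, the plan partly foresees the event. Protocol 9.3 covers a subject who begins a new therapy, but only by ending the safety reporting period. SAP section 7 plans deviation and medication tables and a listing of analgesics used within 24 hours of a visit. These are descriptive, and a Week 8 injection falls outside the 24-hour listing. Handling would then be settled after the data are seen, in a trial meant to be confirmatory.

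**Working it through.** **Inputs from the documents.** Ampion n = 146 and an alternative of 45% (Protocol 10.3.7, SAP 2.4). Null rate 30%, from Protocol 10.3.4: "This test will be tested using an exact binomial test" and "Since this is a one sided test, the alpha level will be 0.025". Earlier KL 4 Ampion responder rate 58.6% combined (Protocol Table 1.5.3).

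**Inputs that are assumptions.** The share of subjects using barred treatment, f, and the share of users who score as responders, q. The documents give neither. I use f = 5% and 10%, and q = 40% to 60%.

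**Step 1: the plan's own figure.** The smallest X with P(X or more | 146, 0.30) ≤ 0.025 is 56, which is 56/146 = 38.4%. The exact error is 0.0189; 55 responders would give 0.0284. Power at 45% is P(56 or more | 146, 0.45) = 95.6%, so the stated power of more than 90% reproduces.

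**Step 2: the current rule, two models.** The chance of passing is P(56 or more | 146, observed rate).

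- Model A: non-users respond at 30%. Observed rate = 0.30(1 − f) + fq.
- Model B: the whole arm would respond at 30% without barred treatment, and every user would otherwise fail. Observed rate = 0.30 + fq. Non-users then respond at 0.30/(1 − f), which is 31.6% at f = 5% and 33.3% at f = 10%.

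| f | q | A: rate | A: chance | B: rate | B: chance |
|---|---|---|---|---|---|
| 0 | – | 30.0% | 1.9% | 30.0% | 1.9% |
| 5% | 40% | 30.5% | 2.6% | 32.0% | 6.1% |
| 5% | 60% | 31.5% | 4.7% | 33.0% | 10.0% |
| 10% | 40% | 31.0% | 3.5% | 34.0% | 15.3% |
| 10% | 60% | 33.0% | 10.0% | 36.0% | 30.4% |

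**Step 3: the PP set.** Suppose all users are classed as major violators and excluded. The PP rate is then the non-users' rate: 30% under A, and 33.3% under B at f = 10%. In the same B case with q = 60%, ITT shows 36%. PP therefore sits below ITT, because it removes the affected responses. It still does not count these subjects as failures. With 44 responders and 15 users scored as failures, the rate is 44/146 = 30.1%; with the 15 removed it is 44/131 = 33.6%. That result would not pass, since 51 of 131 are needed and the one-sided p is 0.21. If the use is not classed as major, the observed scores stay in PP as well.

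**Step 4: counting users as failures.** Tested rate = (non-users' rate) × (1 − f).

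| Non-users' rate | f | Tested rate | Chance of passing |
|---|---|---|---|
| 30% | 5% | 28.5% | 0.6% |
| 30% | 10% | 27.0% | 0.2% |
| 45% | 5% | 42.75% | 87.7% |
| 45% | 10% | 40.5% | 72.9% |
| 58.6% | 20% | 46.9% | 98.5% |

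**The case against.** Keeping violators in an all-randomized set is ordinary ITT practice, and the sentence in Protocol 7.2 is no defect in itself. Using the observed score is a treatment-policy choice; scoring users as failures is a composite choice. Either can be defended. That stands. The fault is that the plan never states the choice, while its primary test has no comparator to absorb the effect.

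There are partial safeguards. A subject who leaves and has no Week 12 score falls under worst observation carried forward, which will often, though not always, give non-response. The planned medication and deviation tables would make use visible. These points also stand, but none of them reclassifies a subject whose Week 12 score was observed.

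The size cannot be checked, because the documents give no rate of use. Model B is the least favourable case, and no passage supports its premise that every user would otherwise fail. Its 6–30% range is therefore one end of the picture, with Model A beside it.

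A reader might infer three stronger things that the documents do not support:

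- That PP repeats the ITT inflation. It does not: where the use is classed as major, PP removes the affected responses.
- That 5.1.11 bars each of these treatments because it would change the scores. Only the item on other systemic treatments mentions interference with assessments.
- That surgery is on the barred list. It is not.

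**Conclusion.** The concern holds as an omission with a direction. Followed as written, the plan lets responses after barred treatment count for Ampion, and no ITT, PP or sensitivity analysis scores those subjects as non-responders. On the milder model the exact error of 1.9% becomes 2.6–4.7% at 5% use and 3.5–10.0% at 10% use. On the harsher model it becomes 6–10% and 15–30%. All of these ranges rest on assumed f and q and on a non-user or whole-arm rate at the null. They show how sensitive the test is and do not predict what happened. A true rate near the earlier 58.6% would leave the primary conclusion little affected either way. The gap matters most when the true rate is close to 30%, which is where the test has to protect.

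**What to change.** In SAP 3.1 and 3.2 and Protocol 10.2, state how treatment barred by 5.1.11 is handled when taken after the study injection and before the Week 12 assessment. The treatments concerned are those that can affect study-knee pain: a study-knee injection, NSAID, opioid, corticosteroid or study-knee topical.

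- Count such a subject as a non-responder in the ITT analysis of the primary and first two secondary endpoints.
- Classify cases from the concomitant medication record before unblinding.
- Report the observed-score analysis as a sensitivity analysis. At a minimum, if observed scores stay primary, pre-specify the non-responder analysis as a named sensitivity analysis.
- For the historic-saline comparison, apply the same rule to both groups where the earlier data allow; otherwise report both versions.
- Define a major protocol violation before unblinding, and leave PP as an exclusion set.

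This changes the analysis only, not which treatments are allowed. Concomitant medication is already recorded at every contact (Protocol Table 6.1), so the work is wording plus a blinded review. The cost is a lower reported response rate and some power. If non-users respond at 45%, power falls from 95.6% to 87.7% at 5% use, or to 72.9% at 10% use, both below the planned 90%. Near 58.6% it stays above 98% up to 20% use.
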